5.7 Inclusion/Exclusion Criteria

4.1 Inclusive criteria:

1. Patients over the age of 18
2. Patients of both sexes
3. Patients who are on anticoagulant therapy
4. Patients with a history of blood disorders

4.2 Exclusion criteria:

1. Patients who are pregnant
2. Patients suffering from mental disease
3. Patients with the HIV virus
4. Patients with a history of anaphylaxis
5. Patients receiving treatment with beta-blockers
6. Patients with sensitivity to bovine proteins
7. Patients with signs of infection
8. Patients who during surgery show signs of sepsis
9. Patients with sensitivity to iodine.

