Several problems exist with the commercially available fibrin sealants: They are a two part system of fibrin and thrombin, which must be mixed at operation or trauma setting, adding to the operative time and delaying transportation to a stable operative setting. Previously, the FDA withheld approval from European products because they used pooled human plasma as a product source¹⁶. The fibrin sealants are somewhat difficult to use, as they must be mixed from four components, a process which takes approximately 15 minutes, and then must be used within four hours. If they are to be used endoscopically, they must be placed through a dual lumen catheter and mixed in situ¹⁷. Their viscosity makes application difficult via catheters and in small areas, and limits methods of application such as sprays, or foams, which would be useful for large wounds. The time between mixing and hemostasis can be several minutes, typically 3-5 minutes, further slowing operation repair¹⁸. The incorporation of fibrin sealants into a dry dressing has reduced some of these problems. The strength of the clot formation, when utilizing a dry dressing, can be sub-optimal. These shortcomings limit the utility of fibrin sealants for hemostasis in the battlefield, emergency response teams such as paramedics, and in the surgical arena.

Bovine topical thrombin in most cases, is a heterologous plasma thrombin concentrate that has been used for hemostasis since the 1940's. Some commercial bovine thrombin preparations are highly immunogenic, and appear to be associated with an increased risk for adverse clinical outcomes during subsequent surgical procedures¹⁹. Antibody formation and anaphylaxis (rates 0.5 to 5.8%) have also been seen with Factor V and aprotinin, a polyvalent proteinase inhibitor isolated from bovine lungs, and used alone to enhance clot stability, or in combination with fibrin sealants^{20,21}. These antibodies may interfere with the heparin anti-Xa assay,

thereby complicating the monitoring of anticoagulant therapy²². The commercially available product, Tisseel VH fibrin sealant, contains bovine aprotinin, resulting in the risk of hypersensitivity²³.

What this study will determine

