Patients receiving treatment at Joaquin Albarran Hospital, Salvador Allende Hospital, and National Institute for Cardio-Vascular Surgery, will serve as study volunteers. Prior to enrollment in the study, an initial screening test and subsequent studies will take place, including: informed consent, collection and recording of subject demographic information, medical history, current medications, assessment of inclusion/exclusion criteria, physical examination, with blood draws for hematological assessment for bleeding and time to hemostasis. The location of the study wounds will be skin-skin. The study wound sites will involve bone and soft tissue.

The primary endpoint in this clinical trial is hemostasis. A Secondary endpoint is the number of surgical cases without a therapeutic break from SeraSeal to a standard surgical modality to control the bleeding. There are 10 designated surgical faculty members from General Surgery, Vascular, Obstetrics and Gynecology participating in this study, with a minimum of 10 surgical procedures being studied. All of the participating surgeons are highly skilled and have extensive expertise in their surgical specialty.

In this trial, the dosage level of SeraSeal vial is 300 IU/0.1ml and 210 IU/pump in the spray, with a maximum expected dosage of 10,000 IU, 20 times less than the pre-clinical toxicity studies. After 1-2 minutes, when hemostasis is achieved, the excess SeraSeal will either be removed through suction or absorption onto a surgical sponge. A time to hemostasis is measured from the time when the product is first applied to the wound, until no bleeding or oozing is observed from the wound. A nurse will use a stopwatch to record the time to hemostasis. SeraSeal will be used from the initial incision and through out the entire surgical procedure, and the time to hemostasis for each bleed will be measured, then totaled for the entire surgery. SeraSeal is expected to achieve a total hemostasis time under 5 minutes. Stopping criteria for treatment will be when hemostasis fails to be achieved after 3 applications for a particular wound, the collective time to hemostasis exceeds 5 minutes, the patient experiences a serious adverse event, or at the surgeons discretion. If this should happen, the patient will be switched over to standard surgical practices.

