The patients will be monitored for post-operative bleeding and overall wound healing for those wounds that can be observed. A base line hemoglobin (HGB), hematocrit (HCT), prothrombin time (PT), partial thromboplastin time (PTT) be drawn, and measured at 24 to 48 hours after surgery. The patients will be observed and assessed for a minimum of 48 hours after application of SeraSeal for signs of post-operative bleeding, and hypersensitivity to the investigational product throughout the hospitalization period. They will be assessed for, but not limited to, skin rash; wheezing; anaphylaxis; pruritus; prolong coagulation tests; delayed healing or infection through quantitative cultures. In the event there is progression of edema leading to respiratory distress, anaphylaxis, or shock due to blood loss, a crash cart and/or any additional standard and customary treatment(s), will be available. This study will not limit the standard of care performed at the four investigational hospitals. The following components of wound care are "standard practice" at each of the hospitals: daily dressing changes; quantitative cultures when infection may be present; routine blood tests. All enrolled study subjects may request to be withdrawn from the study at any time, and will be terminated from the study and provided standard of care. All adverse events will be recorded according to whether the event was unrelated, unlikely, possibly or probably related to the study treatment.

Table 1: Schedule of Assessments

Test	Pre-Op	Surgery	4-8 Hrs Post-Op	24-48 Hrs Post-Op
Informed Consent	X			
History		X		
Physical Examination	X		X	X
HGB	X		X ⁺	X [#]
HCT	X		X ⁺	X [#]
PT	X		X ⁺	X [#]
PTT	X		X ⁺	X [#]
ECG	X		X ⁺	X [#]
Radiological work-up	X		X ⁺	X [#]
Adverse Events		X	X	X [#]
Effectiveness		X	X	X
Safety		X	X	X

+ measured as often as needed.

monitored beyond 48 hours and as needed

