6.3 Safeguards for Protecting Subjects: The risks of SeraSeal treatment are minimized by the patient selection process. Should an allergic reaction occur, the participant will be withdrawn from the study and standard of care administered. Physicians, nurses, and technicians, will be on hand for all procedures. Patients will be monitored through routine post-operative care. Should any adverse event occur during treatment, immediate intervention is possible. A crash cart is kept in the treatment room and on the hospital floor. Patient records will be kept confidential.

6.4 Alternatives: Alternatives to SeraSeal are the application of no hemostatic agents, electric cauterization, ligature, pressure dressings, collagen dressings, and the use of fibrin sealants. The application of other dressings containing proteins, carries the risk of allergic reaction.

7.0 Data Analysis:

7.1 Data Collection: There will be one study form for each patient. The surgery form will have all of the outcome data and adverse events. Once the patient's surgical procedure qualifies for the study, the patient will be asked to participate in the clinical trial by the participating investigator surgeon. The only patients that will require special action are the SeraSeal patients. For those patients the need for SeraSeal will be made known only to the attending surgeon and/or fellows, and made available to the OR room. At the time of the pre-op exam, the inclusion/exclusion of participation in the study will be filled out. The monitor board member will collect all data forms and will be responsible for evaluating them for completeness and accuracy, except for time to hemostasis supplied by the surgeon.

7.2 Statistical Analysis: We will compare continuous outcomes such as time to hemostasis (primary outcome), and therapeutic breaks from SeraSeal to standard surgical modalities to control bleeding. This study will use a relatively simple method of analyzing the data generated by employing a non-parametric statistical analysis,

using the chi-square distribution.

For continuous lab outcomes measured on two occasions (base, 24- 48 hours), we will use repeated measure analysis of variance methods to compare mean lab values for conventional versus SeraSeal® overall.

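### PT and PTT are compared overall from baseline to 24-48 hours in a population that includes anticoagulated patients, with no recording of exposure around the two draws, so a change in anticoagulant use can mask or mimic a product effect

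*Protocol*

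**What the plan says.** **Eligibility.** Section 5.7, inclusion item 3, reads "Patients who are on anticoagulant therapy", and item 4 reads "Patients with a history of blood disorders". No agent is named, and nothing says what exposure is expected at either blood draw.

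**Recording.** Section 5.6 lists, before enrolment, "medical history, current medications, assessment of inclusion/exclusion criteria". No later recording of anticoagulant exposure is stated. Section 5.6 also leaves care to each hospital's standard, and section 7.1 provides one study form per patient.

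**Measurement.** Section 5.6 calls for a baseline "prothrombin time (PT), partial thromboplastin time (PTT) be drawn, and measured at 24 to 48 hours after surgery". Table 1 agrees, with a 4-8 hour measurement only as often as needed. Among the things patients are assessed for, section 5.6 names "prolong coagulation tests".

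**Analysis.** For laboratory values on the two occasions, section 7.2 states "we will use repeated measure analysis of variance methods to compare mean lab values" for conventional against SeraSeal treatment, overall. It gives no stratum, covariate or exclusion for anticoagulant use. Section 5.6 describes the study as non-randomized and unblinded, with standard methods in historically known cases as the comparison.

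**The concern.** PT and PTT are the only coagulation tests scheduled, and section 5.5 describes SeraSeal as acting on both the intrinsic and extrinsic pathways. A change in these tests is therefore a sensible thing to look for. But an anticoagulant moves the same tests. A patient exposed at the baseline draw and unexposed at the second will tend to show a fall. A patient unexposed at baseline and exposed again by 24-48 hours will tend to show a rise. Neither change says anything about the product.

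A single overall mean mixes these changes with any product effect. Randomization would make the handling of anticoagulants similar in the two groups on average; here nothing does. At stake is the reading of a secondary safety measurement: a real prolongation could be missed, or a false one reported. If exposure around the draws is not captured at the time, no later analysis can reliably separate the two explanations.

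**Working it through.** **Inputs from the protocol.** There are two occasions (section 7.2) and 120 subjects (section 5.9). No anticoagulated share, PT shift, PT standard deviation or size of conventional group is given.

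**The protocol's own figure.** The 120 reproduces as a precision calculation for a proportion with finite-population correction, if p = 0.5 is assumed: n0 = 1.96² × 0.25 / 0.05² = 384.1, and n = 384.1 / (1 + 383.1/175) = 120.4. It rests on time to hemostasis, not on PT or PTT. The present point does not depend on it, except as the group size in step 3.

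**Step 1: shift within the SeraSeal group.** Let f be the share of patients whose exposure differs between the draws and s their mean PT change from that cause (negative if stopped, positive if restarted). The group mean change moves by f × s. All inputs below are assumed.

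| f | Size of s | Shift in mean change |
|---|---|---|
| 5% | 2 s | 0.1 s |
| 10% | 3 s | 0.3 s |
| 20% | 5 s | 1.0 s |
| 30% | 8 s | 2.4 s |

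Masking: with f = 20% and s = −5 s the shift is −1.0 s, which cancels an assumed true prolongation of 1.0 s in every patient.

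**Step 2: bias in the planned contrast.** Section 7.2 compares two groups. The difference in mean change is biased by f_S × s_S − f_C × s_C, with S for SeraSeal and C for conventional. If handling is identical, this is zero. If, for example, f_S = 20%, f_C = 10% and s = 5 s in both, it is 1.0 − 0.5 = 0.5 s. The documents give neither term, so the bias can be anywhere from nothing upward, in either direction.

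**Step 3: how easily a false signal could arise within one group.** This uses a one-sample z approximation, which is not the planned test. Take n = 120, an assumed SD of change of 2 s, no product effect, and restart shifts of s = 5 s. The SD of change becomes √(2² + f(1−f)s²), and the probability of a significant prolongation is Φ(f·s/SE − 1.96).

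- f = 5%: SD 2.28 s, shift 0.25 s, probability 0.22.
- f = 10%: SD 2.50 s, shift 0.50 s, probability 0.59.
- f = 25%: SD 2.95 s, shift 1.25 s, probability 0.996.
- Small case, f = 5% and s = 2 s: SD 2.05 s, shift 0.10 s, probability 0.08.

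**The case against.** **The planned analysis is between groups, not a pooled change in one arm.** This stands. Only a difference in handling biases the stated contrast, so the within-group figures cannot be read as the bias in the result. But in a non-randomized comparison with historical practice, nothing in the protocol makes handling alike.

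**Strata and covariates belong in the SAP.** This is partly right, and an SAP may exist. But the protocol itself commits to an overall comparison, and the gap is also in data capture: an SAP cannot adjust for exposure that was not recorded. The form is not shown, so one can say only that the protocol states no such recording.

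**Prolonged tests can be judged patient by patient.** Section 5.6 has adverse events graded by relatedness, and section 7.2 sends binary outcomes to chi-square methods. That helps with individual cases but does not repair the comparison of means.

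**The size is wholly assumed.** True. At the low end it is trivial, and stops and restarts in the same group would partly cancel in the mean.

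Three stronger readings are tempting, and the documents do not support them.

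- A reader might infer that eligibility lacks a time window. The criterion is in the present tense and means current use at entry. What is undefined is exposure at the two draws, and an eligibility window would not cure that.
- A reader might infer that the trial's main safety conclusion is at risk. Section 5.5 defines safety by recurrent bleeding, infection, lack of healing and hypersensitivity; PT and PTT are not in that list.
- A reader might take the remark in section 5.5 that antibodies may end up "thereby complicating the monitoring of anticoagulant therapy" as support. It concerns the heparin anti-Xa assay and follows a sentence on Factor V and aprotinin, neither of which SeraSeal contains according to section 6.2.

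**Conclusion.** The point holds for PT and PTT as secondary safety measurements. Patients on anticoagulants are admitted, exposure after screening is not stated to be recorded, and the overall comparison cannot tell a product effect from a change in anticoagulant use. The possibility of error in both directions follows from the text, together with the fact that anticoagulants act on these tests. Its size does not. The within-group shift of about 0.1-2.4 s rests on assumed shares of 5-30% and assumed PT shifts of 2-8 s, and the between-group bias also depends on the unknown handling in the conventional group.

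The finding survives either reading of the inclusion list. If items 3 and 4 mean that such patients are also eligible, the population is mixed. If they are literal requirements, every patient is anticoagulated and the potential bias is larger. It does not reach the time-to-hemostasis result through this route.

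**What to change.** Before enrolment, add three items to the existing study form: the anticoagulant agent, the last dose before the baseline draw, and any dose before the 24-48 hour draw.

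In section 7.2, replace the single overall PT/PTT comparison with the change from baseline to 24-48 hours reported by anticoagulant status at the two draws: none, unchanged, stopped, restarted. Give counts newly above the normal range in each category.

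Reporting by status is preferable to restricting the main analysis to patients without anticoagulants. At an anticoagulated share of 30%, that restriction would remove 0.30 × 120 = 36 patients, and under the literal reading of item 3 it could leave almost no one. Reporting by status works under both readings. It does not deal with coagulation changes due to blood disorders under item 4.

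The cost is a few form fields, one extra table and smaller numbers per stratum, so some categories may support description only. Eligibility and patient care are unchanged.

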12.1 STUDY INFORMATION

12.1.1 Protocol

Study No.: WLI-4306-HAV

Clinical Investigation – Havana, Cuba

1. **Title:** SeraSeal, A Primary hemostatic Agent, Clinical Study
2. **Principal Investigator:** [name] [name]
[name] [name]
[name] [name]
[name] [name]
[name] [name]
[name] [name]
[name] [name]
[name] [name]
[name] [name]
[name] [name]
3. **Monitors:** [name] [name]
[name] [name]
[name] [name]
4. **Identification of the Research:** This study focuses on treatment of bleeding wounds
4. **Location:** Joaquin Albarran Hospital, Havana, Cuba
Salvador Allende Hospital, Havana, Cuba
National Institute for Cardio-Vascular Surgery, Havana, Cuba

5. Research Plan:

5.1 Purpose: SeraSeal was designed as a primary hemostatic agent to control all forms of bleeding. In this study, SeraSeal is to be applied from the initial incision, and throughout the entire surgical procedure to closing without any intervention of standard surgical methods to control bleeding. Only one delivery system, syringe or spray of SeraSeal is to be used for that particular surgical case without any cross-over.

5.2 Hypothesis or Research Questions or Objectives: The null hypothesis is that SeraSeal will not be more effective than surgical modalities to control bleeding in surgical cases historically known to take more than 6 minutes to control all of the hemorrhages. The alternative hypothesis is that SeraSeal will have a collective time to hemostasis of less than 5 minutes in 95% of the surgical cases.

5.3 Significance: SeraSeal shows promise of being a superior hemostatic agent applicable to wounds, surgical operations in which hemostasis is difficult (hepatic, renal and splenic trauma, debridement, burns, skin grafting, endoscopic procedures), control of epistaxis, esophageal variceal bleeding, bleeding peptic ulcers, and bleeding associated with proctitis and cystitis. For some of these conditions, there is no entirely satisfactory treatment.

5.4 Relevance: The availability of an easy to use, stable, safe, effective hemostatic agent, would be a tremendous advantage to the trauma patient (surgical or accidental), possibly reducing morbidity and mortality significantly, and conserving surgical and blood resources.

5.5 Background and Review of Literature:

Problem with Bleeding Wounds

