This study is designed to determine whether SeraSeal is effective as a primary hemostatic agent, and safe in achieving hemostasis in surgical wounds or other emergent hemorrhagic episodes. The effectiveness will be determined by achieving hemostasis after application of the product. The safety will be determined by monitoring outcomes from application: recurrence of bleeding, infection, lack of healing, and presence of hypersensitivity reactions, e.g. pruritus, fever, rash, anaphylaxis.

Characteristics of SeraSeal

SeraSeal is a bovine protein-derived accelerator of hemostasis interacting with the intrinsic and extrinsic pathways. It is obtained from pathogen and prion free cows. SeraSeal can be provided as a solution, spray, foam, incorporated into an absorbable dressing or a non-absorbable removable dressing. Its active ingredients are Factors IIa, VIIa, IXa, and Xa.

Toxicity of SeraSeal

A total dosage level of SeraSeal over 13,000 IU/Kg (2.4 mg protein) in leporids and canines had no adverse effects^{24,25}. The total expected treatment levels to be used in this study is less than 1,000 IU/Kg, a thirteen fold lower level than the no toxic effect. Thus, drug related toxicity is not expected to be seen in this clinical study. Cell culture studies reveal that SeraSeal is not directly toxic for any cells tested.

5.6 Research Design and Methods: This clinical trial will be a non-randomized, unblinded study where SeraSeal will be used as a liquid, administered by a syringe (300 IU/0.1ml) or spray (210 IU/pump), and compared to standard surgical methods to control bleeding in historically known surgical cases taking more than 6 minutes to control all of the hemorrhages. The intent-to-treat patients will be placed into either the SeraSeal syringe treatment group, where bleeding from medium to large blood vessels may occur, or the SeraSeal spray treatment group, where only capillary to small blood vessels would be treated with the investigational product.

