5.8 Source of Research Material

5.9 Number of Subjects: A total of 120 subjects, are to participate in this study.

6.0 Recruitment: Subjects will be selected from within each participating surgical department at Joaquin Albarran Hospital, Salvador Allende Hospital, and National Institute for Cardio-Vascular Surgery. The faculty from each hospital will obtain an informed consent, prior to their participation in the study. No promotional fliers are planned. The consent form will be provided by both hospitals in Spanish. Subjects will not be paid for participation in this study.

6.1 Benefits: The possible benefit of the patient's participation in this study is a faster time to clotting, less blood loss, faster wound healing, and less loss of tissue. However, the participant should understand there is no guarantee or promise that they will receive any benefit from this study, other than knowing that the information may help future patients.

6.2 Risks: The risks of application of SeraSeal are theoretical. These risks may be bleeding, infection, and allergic reaction. Anaphylaxis is a possible risk, but the incidence is not clearly known. Aprotinin, a bovine protein derived from the bovine lung, is used in cardiac surgery and is the component of some fibrin sealants. It has an anaphylaxis rate of 2.5% on second exposure, with a mean interval of 1,654 days (range, 16-7,136 days)²⁶. SeraSeal contains no aprotinin. Bovine gelatin is a component of some vaccines and anaphylaxis has been reported with this protein²⁷. Other bovine proteins for which anaphylaxis and hypersensitivity reactions have been reported, are bovine serum albumin²⁸, thrombin^{29,30}, recombinant Factor VIII³¹, insulin³², and tissue sealants³³. The risk of anaphylaxis appears to be lower for topical devices than injected ones, and repeated administration with a break, as proposed in this study, also appears to have a lower incidence of anaphylaxis²⁴. We surmise that anaphylaxis may be a risk of application of SeraSeal. Measures to reduce and treat anaphylaxis is to exclude those patients who are sensitive to bovine proteins from the study, and to provide a crash cart, and/or any additional standard and customary treatment(s). One of the purposes of this study is to determine that risk. Reports of an autoimmune reaction to fibrin sealants containing bovine Factor V mimicking hemophilia have been reported. SeraSeal does not contain Factor V.

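### Exclusion item 8 can only be met once SeraSeal is normally already in use, and section 6.3 ends study participation after an allergic reaction: treated patients can drop out of the study and later safety follow-up can be lost

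*Protocol*

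**What the plan says.** **Exclusion during surgery.** Item 8 of the exclusion list in Protocol section 5.7 reads "Patients who during surgery show signs of sepsis". Item 7 already excludes patients with signs of infection, so what item 8 adds is the time in the operating room.

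**Start of exposure.** Section 5.1 states that "SeraSeal is to be applied from the initial incision, and throughout the entire surgical procedure to closing", and section 5.6 repeats that "SeraSeal will be used from the initial incision and through out the entire surgical procedure".

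**Timing of the eligibility check.** Section 5.6 says "Prior to enrollment in the study, an initial screening test and subsequent studies will take place" and names the assessment of the inclusion and exclusion criteria among these steps. Section 7.1 says "At the time of the pre-op exam, the inclusion/exclusion of participation in the study will be filled out".

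**Allergic reaction.** Section 6.3 says "Should an allergic reaction occur, the participant will be withdrawn from the study and standard of care administered". Section 5.5 names as safety outcomes "recurrence of bleeding, infection, lack of healing, and presence of hypersensitivity reactions". Section 6.2, on anaphylaxis, adds "One of the purposes of this study is to determine that risk".

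**Serious adverse events.** Section 5.6 makes a serious adverse event a criterion for stopping treatment, with a switch to standard surgical practice. It does not mention leaving the study there.

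**The concern.** An eligibility criterion should depend only on what is known before treatment. Item 8 depends on something seen during the operation, after the product has normally been applied. A patient who meets it is a treated patient who is then declared ineligible. The trial is unblinded, so the bleeding result can be visible when that judgment is made, and section 5.7 does not define signs of sepsis. The finding is also close to infection, one of the outcomes by which safety is judged.

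The allergy rule raises a different problem. Patients with a reaction are the ones whose later course matters most for a stated purpose of the study. Section 6.3 takes them out of the study, not only off the product. Section 5.6 says that subjects who ask to withdraw are terminated from the study and given standard care, which suggests that withdrawal here means the end of participation.

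At stake are the denominator of the success rate, the count of infections, and the follow-up of patients with a reaction.

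**Working it through.** **1. Timing of item 8.**

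| Step | Section | Can item 8 be judged? |
|---|---|---|
| Screening before enrollment | 5.6 | No |
| Eligibility form at the pre-op exam | 7.1 | No |
| First incision, SeraSeal begins | 5.1, 5.6 | Only from here on |
| Rest of surgery, SeraSeal in use | 5.1, 5.6 | Yes |

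The protocol's own eligibility check is finished before item 8 can arise, so the sections contradict each other. Item 8 works as a removal after exposure.

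**2. The plan's sample size.** Section 7.2 gives 120 patients from 175 cases per day, 95% confidence and a margin of 5 points. The formulas are n0 = z²p(1−p)/d² and n = n0/(1 + (n0 − 1)/N). With p = 0.5, d = 0.05 and N = 175:

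- n0 = 1.96² × 0.25/0.0025 = 384.1
- n = 384.1/(1 + 383.1/175) = 120.4

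The figure of 120 is reproduced without any allowance for patients removed after treatment. It has no other bearing on this point.

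**3. What removals could do to the success rate.** The alternative hypothesis in section 5.2 sets the target at 95% of cases. The protocol gives no expected number of sepsis findings, so the counts below are assumptions. Suppose 120 patients are treated, F of them are failures, and k failures are removed. The reported rate is (120 − F)/(120 − k).

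| F | k = 0 | k = 2 | k = 3 | k = 4 | k = 6 |
|---|---|---|---|---|---|
| 6 | 114/120 = 95.0% | 96.6% | 97.4% | 98.3% | 100% |
| 9 | 111/120 = 92.5% | 94.1% | 94.9% | 95.7% | 97.4% |
| 12 | 108/120 = 90.0% | 91.5% | 92.3% | 93.1% | 94.7% |

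With 9 failures, removing 4 (4/120 = 3.3% of the sample) moves the estimate across the target. The exact 95% interval goes from 86.2–96.5% to 90.2–98.6%. With 12 failures, even 6 removals do not reach 95%.

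If the 4 removed patients were successes instead, 111/120 would become 107/116 = 92.2%, a small change downwards. The table is therefore the adverse case, not a forecast.

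**4. What is lost after an allergic reaction.** Section 5.6 requires all adverse events to be recorded, Table 1 collects them from surgery onward, and section 7.1 puts them on the surgery form. The reaction itself is therefore to be captured. What can be lost comes later:

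- the course of the reaction, wound healing and re-bleeding
- the 24–48 hour laboratory values
- the rest of the 30-day participation in section 8

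**5. Two rules for one patient.** A serious allergic reaction during surgery meets both the stopping rule in section 5.6 (switch to standard practice) and the rule in section 6.3 (withdrawal from the study). The protocol does not say which consequence applies to the patient's place in the study.

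**The case against.** The strongest reply is that the protocol nowhere drops excluded or withdrawn patients from the analysis. Analysis sets are commonly left to an SAP, which may exist. This stands as far as it goes: removal from the denominator is a consequence of applying item 8 as written, not a stated analysis rule. An SAP could not fully repair it, though. Keeping patients whom section 5.7 excludes would contradict the protocol, and follow-up that section 6.3 ends cannot be recovered in the analysis.

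Item 8 may also be meant for infection that was already present and is first recognized at operation, which would be a baseline condition. That is a fair reading of its purpose, but the text does not limit the item to findings before first application.

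A reader might infer three stronger things that the documents do not support:

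- **That hypersensitivity cases disappear from the data.** Sections 5.6 and 7.1 require the events to be recorded. An example such as 3/120 = 2.5% turning into 0/117 needs the recorded events to be deleted, which no section says.
- **That patients with sepsis are likely hemostasis failures, so the success rate is inflated.** This is plausible, but no section links sepsis to failed hemostasis.
- **That the rules breach a defined intent-to-treat analysis.** Section 5.6 uses the term only when placing patients in the syringe or spray group and defines no analysis set.

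**Conclusion.** The point holds in limited form. Item 8 is an exclusion after exposure and contradicts the timing of the eligibility check in sections 5.6 and 7.1. Section 6.3 can end follow-up for patients whose risk section 6.2 sets out to determine. Both follow from the protocol's text and need no assumed number.

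The effect on the success rate is unknown in direction and size. The move from 92.5% to 95.7% rests on 9 assumed failures among 120, of whom 4 are removed. It shows only that a 95% target leaves little room for removals that depend on what happened in surgery. For hypersensitivity, the loss shown is later follow-up, not the event count. If a reaction occurs during surgery, the hemostasis result may also be incomplete.

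This should be corrected, because the change is cheap and removes an avoidable source of bias.

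**What to change.** - **Section 5.7:** limit the eligibility criteria to what is known before the first SeraSeal application, in line with sections 5.6 and 7.1.
- **Analysis:** keep every patient who receives any SeraSeal in the effectiveness and safety analyses. Record signs of sepsis during surgery as an adverse event, and repeat the main analysis without these patients as a sensitivity analysis.
- **Endpoints:** count any resulting switch as a therapeutic break under the existing secondary endpoint, and score the primary endpoint by its own definition. A switch should not automatically become a primary failure, because section 5.6 treats hemostasis and therapeutic breaks as separate endpoints.
- **Section 6.3:** separate stopping the product from leaving the study, and continue data collection to the end of follow-up unless consent is withdrawn.
- **Sections 5.6 and 6.3:** reconcile what happens to the study participation of a patient with a serious allergic reaction.

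These changes concern eligibility, data collection and analysis. The clinical management of sepsis and of allergic reactions stays as it is. The cost is a few wording changes, routine recording for a few more patients, and a success rate that may come out slightly lower.
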